	
SCLC) will be followed-up at least every six months and up to 12 months after the last patient enrolled received the first PM01183 infusion (a documented phone contact will be acceptable). Patients in the SCLC cohort, after PD, will be followed-up every six months for at least 18 months after the last patient enrolled received the first PM01183 infusion (a documented phone contact will be acceptable).
 
Patients will be considered to be on-study from the signature of the informed consent form (ICF) until the end of the follow-up period. Patients will be considered to be on-treatment for the duration of their treatment and until the day of EOT, immediately before the start of the follow-up period. This EOT is defined as 30 days after the day of the last PM01183 infusion, unless the patient starts a new antitumor therapy or dies (whichever occurs first). An end-of-treatment visit (EOT visit) will be performed within 30 days (± 7 days) after the last study treatment administration, unless the patient starts any subsequent antitumor therapy, in which case the EOT visit should be performed immediately before the start of the new therapy.
 
Patients will receive the study treatment while it is considered to be in their best interest. Specifically, treatment will continue until:
 
 • Disease progression. • Unacceptable toxicity. • Treatment delay > three weeks from the treatment due date (except in case of clear clinical benefit, upon Sponsors' approval). • Requirement of > two dose reductions. • Intercurrent illness of sufficient magnitude to preclude safe continuation of the study. • A major protocol deviation that may affect the risk/benefit ratio for the participating patient. • Investigator's decision. • Non-compliance with study requirements. • Patient's refusal.

PLANNED TRIAL PERIODS (for the whole study)
	
The total duration of the study will be approximately 52 months, including approximately a 40-month enrolment period.
 
Planned start date (first patient on study): 3Q2015.
 
Planned enrolment period: 40 months.
 
Planned end-of-study date (clinical cutoff for each cohort except SCLC): when all evaluable patients within each cohort have at least 12 months of follow-up from the first PM01183 infusion. Patients in the SCLC cohort will be followed-up for at least 18 months after the last patient enrolled received the first PM01183 infusion.

SCHEDULE OF ASSESSMENTS AND PROCEDURES

Assessments and procedures	Screening* (days)	Treatment								Follow-up
		Cycle 1			Cycle 2			Further cycles	End of treatment (EOT) ‡	
		D1	D8	D15	D1	D8	D15			
Written informed consents (general and PGx/pharmacogenetic sub-study)	Before any study procedure	-	-	-	-	-	-	-	-	-
Demographic data	-28 to 0	-	-	-	-	-	-	-	-	-
Primary diagnosis and prior treatment(s)	-28 to 0 (+1 week)	-	-	-	-	-	-	-	-	-
Medical and cancer history/baseline conditions	-14 to 0 (+1 week)	-	-	-	-	-	-	-	-	-
Assessment of disease signs and symptoms	-7 to 0 (+1 day)	-	-	-	-	-	-	-	-	-
Complete physical examination, including weight and height and calculation of BSA ⁽¹⁾	-7 to 0 (+1 day)	•	-	-	•	-	-	•	•	-
ECOG PS	-7 to 0 (+1 day)	•	-	-	•	-	-	•	•	-
Vital signs (heart rate, blood pressure, temperature)	-7 to 0 (+1 day)	•	-	-	•	-	-	•	•	-
Coagulation panel	-7 to 0	-	-	-	•	-	-	•	•	-
Hematology ^(2,3) †	-7 to 0	• (4)	•	•	•	•	•	• (5)	•	-
Biochemistry A ⁽²⁾ †	-7 to 0	-	•	•	•	•	•	• (5)	•	-
Biochemistry B †	-7 to 0	-	-	-	•	-	-	•	•	-
Pharmacokinetics and AAGP	-	• (6)	-	-	• (7)	-	-	-	-	-
Pharmacogenetic sub-study (only if written informed consent given)	One blood sample collected at any time during the study, but preferably just before treatment start in Cycle 1									-
Pharmacogenomic (PGx) sub-study (only if written informed consent given)	Available stored paraffin-embedded tumor tissue samples, assessed at any time during the study.									-
Pregnancy test ⁽⁸⁾ †	-7 to 0	•	-	-	•	-	-	•	•	-
ECG ⁽⁹⁾	-7 to 0 (+3 days)	Repeat if clinically indicated								-
LVEF by ECHO or MUGA ⁽⁹⁾	-28 to 0 (+3 days)	Repeat if clinically indicated								-
Radiological tumor assessment ⁽¹⁰⁾	-28 to 0 (+1 week)	Every two cycles from the onset of the study treatment until Cycle 6 and every three cycles thereafter ⁽¹¹⁾								• ⁽¹²⁾
Concomitant therapies	-14 to 0 (+1 week)	Throughout the "on-treatment period"								-
Adverse events	- §	Throughout the "on-treatment period"								• ⁽¹³⁾

*Screening procedures will have to be repeated in case that the first infusion of the study treatment is given out of the established windows.

6. Eight blood samples (before PM01183 infusion start, 5 min before the end of PM01183 infusion and 30 min, 1 hour, 3 hours, 24 hours, 72 hours and 168 hours after the end of PM01183 infusion) will be collected for pharmacokinetic analyses in Cycle 1. In addition, one blood sample for the evaluation of AAGP will be collected before PM01183 infusion start.
7. Six blood samples (before PM01183 infusion start, 5 min before the end of PM01183 infusion and 30 min, 1 hour, 3 hours and 168 hours after the end of PM01183 infusion) will be collected for pharmacokinetic analyses in Cycle 2. In addition, one blood sample for the evaluation of AAGP will be collected before PM01183 infusion start.
8. Beta subunit-human chorionic gonadotropin (β -hCG) (urine or serum). In patients of childbearing potential (except germ cell tumor patients), if β -hCG levels are elevated, pregnancy must be clinically discarded by an additional test (i.e., ultrasound) before any other study procedure. Pregnancy during treatment or within three months from the patient's last PM01183 administration is considered an immediately reportable event.
9. ECG: cardiac rhythm will be identified in ECG intervals of at least 30 seconds of duration, PR interval, QT interval (raw), heart rate (HR) and QRS complex. LVEF: impaired cardiac function is defined as LVEF $< 50\%$ as measured by multiple-gated acquisition scan (MUGA) or echocardiography (ECHO).
10. Evaluation by contrast enhanced helical CT-scan or MRI, as clinically indicated, of all measurable sites of disease involvement and of all non-measurable sites of disease should be done at baseline. While on treatment, evaluation of all original sites of disease involvement at baseline should be done as per RECIST v.1.1. Evaluation should be repeated at end of treatment visit, if not previously done, and if the reason for treatment discontinuation is other than PD. The same initial method must be used throughout the study. In SCLC patients, brain CT-scan or MRI will be requested at baseline within two weeks before the planned treatment onset to rule out CNS involvement. In SCLC patients, anonymized copies of all the images obtained throughout the study must be submitted to the Sponsor.
11. Patients showing a response must have a confirmatory assessment at least four weeks later.
12. Only patients who discontinue treatment without PD will have radiological evaluations. The assessments will be performed every two months during the first six months and every three months thereafter until PD, start of a new antitumor therapy, death, or until the date of study termination (clinical cutoff for each cohort except SCLC: when all evaluable patients within each cohort have at least 12 months of follow-up from the first PM01183 infusion). Patients with SCLC will be followed-up for at least 18 months after the last patient enrolled received the first PM01183 infusion (a documented phone contact will be acceptable).
13. Patients withdrawn from the study treatment with an ongoing drug-related AE should be followed every four weeks until event recovery to at least grade 1 or stabilization or until onset of a new antitumor therapy.

Coagulation: PT/INR and PTT.

Hematology: Hemoglobin, platelet counts, and differential WBC including neutrophils, monocytes and lymphocytes.

Biochemistry A: Serum electrolytes (Na^+ , K^+ , Cl^-), AST, ALT, AP, GGT, total bilirubin (direct bilirubin to be measured only if total bilirubin is $>1.5 \times \text{ULN}$), LDH, creatinine, glucose, and CPK.

Biochemistry B: Albumin, total proteins, total calcium and Mg^{++} . Albumin assessments on Day 1 of every cycle during the study are mandatory for all patients. Total proteins, total calcium and Mg^{++} will be measured at baseline and repeated thereafter only in those patients with abnormal baseline values.

In patients with germ cell tumors, β -hCG and AFP will be measured at baseline and repeated thereafter in those patients with elevated values at baseline.

AAGP, alpha-1 acid glycoprotein; AFP, alpha fetoprotein; AE(s), adverse event(s); ALT, alanine aminotransferase; AP, alkaline phosphatase; AST, aspartate aminotransferase; β -hCG, beta subunit of human chorionic gonadotropin; CNS, central nervous system; CPK, creatinine phosphokinase; CPK-MB, creatinine phosphokinase MB isoenzyme; CT, computed tomography; ECG, electrocardiogram; ECHO, echocardiogram; ECOG PS, Eastern Cooperative Oncology Group performance status; EOT, end of treatment; GGT, gamma glutamyltransferase; HCG, human chorionic gonadotropin; HR, heart rate; ICF, informed consent form; INR, international normalized ratio; LDH, lactate dehydrogenase; LDL, low density lipoprotein; LVEF, left ventricular ejection fraction; MRI, magnetic resonance imaging; MUGA, multiple gated acquisition scan; NA, not applicable; NCI-CTCAE, National Cancer Institute Common Terminology Criteria for Adverse Events; PD, progressive disease; PGx, pharmacogenomics; PK, pharmacokinetic(s); PT, pro-thrombin time; PTT, partial thromboplastin time; SCLC, small cell lung cancer; WBC, white blood cells.

LIST OF ABBREVIATIONS AND DEFINITION OF TERMS

1y-OS	One-year Overall Survival
5-FU	5-Fluorouracil
5-HT₃	Serotonin
AAGP	Alpha-1 Acid Glycoprotein
AE(s)	Adverse Event(s)
AFP	Alpha-Fetoprotein
ALT	Alanine Aminotransferase
ANC	Absolute Neutrophil Count
AP	Alkaline Phosphatase
ASCO	American Society of Clinical Oncology
AST	Aspartate Aminotransferase
β-hCG	Beta Subunit of Human Chorionic Gonadotropin
BEP	Bleomycin, Etoposide and Cisplatin
BSA	Body Surface Area
C_{max}	Maximum Plasma Concentration
CAV	Cyclophosphamide, Doxorubicin (Adriamycin) and Vincristine
CNS	Central Nervous System
CPK	Creatine Phosphokinase
CR	Complete Response
CRA	Clinical Research Assistant
CRF	Case Report Form
CSF	Colony-stimulating Factors
CT	Computed Tomography
d/D	Day(s)
DNA	Deoxyribonucleic Acid
DP	Drug Product
DR	Duration of Response
DSB	Double-strand Breaks
ECG	Electrocardiogram
ECHO	Echocardiography
ECOG	Eastern Cooperative Oncology Group
EFTs	Ewing Family of Tumors
EGF	Epidermal Growth Factor
EGFR	Epidermal Growth Factor Receptor
EOI	End of Infusion
EOT	End of Treatment
EPO	Erythropoietin

EU	European Union
FD	Flat Dose
FDA	Food and Drug Administration
FUP	Follow-up
GCP	Good Clinical Practice
GCTs	Germ Cell Tumors
GDPR	General Data Protection Regulation
GEP-NETs	Gastroenteropancreatic Neuroendocrine Tumors
GGT	Gamma Glutamyltransferase
GMT	Greenwich Meridian Time
Gy	Gray
H&N	Head and Neck Carcinoma (Cancer)
hCG	Human Chorionic Gonadotropin
HER-2	Human Epidermal Growth Factor Receptor 2
HIV	Human Immunodeficiency Virus
HR	Hazard Ratio/Homologous Recombination
IA	Investigator's Assessment
IB	Investigator's Brochure
IC	Informed Consent
IC₅₀	Half Maximal Inhibitory Concentration
ICF	Informed Consent Form
ICH	International Conference on Harmonization
IEC	Independent Ethics Committees
IG₅₀	Concentration that Results in 50% of Cell Growth Inhibition
IHC	Immunohistochemistry
IMP	Investigational Medicinal Product
INR	International Normalized Ratio
IRB	Institutional Review Board
IRC	Independent Review Committee
irPFS	Immune-related PFS
i.v.	Intravenous (ly)
LC-MS/MS	Liquid Chromatography/Mass Spectrometry/Mass Spectrometry
LDH	Lactate Dehydrogenase
LVEF	Left Ventricular Ejection Fraction
MAb	Monoclonal Antibody
MBC	Metastatic Breast Cancer
mg	Milligram
MRI	Magnetic Resonance Imaging
mTOR	Mammalian Target of Rapamycin

MUGA	Multiple-gated Acquisition Scan
NCCN	National Comprehensive Cancer Network
NCI	National Cancer Institute
NCI-CTCAE	National Cancer Institute-Common Terminology Criteria for Adverse Events
NER	Nucleotide Excision Repair
NET(s)	Neuroendocrine tumor(s)
NSCLC	Non-small Cell Lung Cancer
ORR	Overall Response Rate
OS	Overall Survival
PARP	Poly (ADP-Ribose) Polymerase
PCR	Polymerase Chain Reaction
PD	Progressive Disease/Disease Progression
PFS	Progression-free Survival
PhV	Pharmacovigilance
PGx	Pharmacogenomics
PK	Pharmacokinetics
PM01183	Lurbinectedin
PNET	Peripheral Neuroectodermic Tumor
PR	Partial Response
PRBC	Packed Red Blood Cells
PRE TT	Pre-treatment
PS	Performance Status
PT	Pro-thrombin Time
PTEN	Phosphatase and Tensin Homolog
PTT	Partial Thromboplastin Time
q3wk	Every Three Weeks
Q7dx3	Three Consecutive Weekly Doses (D-0,7,14)
Qdx5x2	Two Cycles of Five Daily Doses
RBC(s)	Red Blood Cell(s)
RD	Recommended Dose
RECIST	Response Evaluation Criteria In Solid Tumors
RR	Response Rate
RT	Radiotherapy
SAE(s)	Serious Adverse Event(s)
SCLC	Small Cell Lung Cancer
SD	Stable Disease
SUSAR/SUA	Suspected Unexpected Serious Adverse Reaction
T/C	Treatment/Control
TAP	Cisplatin, Doxorubicin, plus Paclitaxel

TIP	Paclitaxel, Ifosfamide and Cisplatin
TT	Treatment
TTP	Time to Progression
UK	United Kingdom
ULN	Upper Limit of Normal
US/USA	United States/United States of America
VIP	Etoposide, Ifosfamide and Cisplatin (Vinblastine-based)
WBC	White Blood Cells
WHO	World Health Organization
wk/wks	Week/weeks
WOCBP	Women of Childbearing Potential
WMA	World Medical Association

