	
♦ Biochemistry B: Albumin, total proteins, total calcium and Mg⁺⁺. In patients with germ cell tumors, β-hCG and AFP only in those patients with elevated values at baseline.
	
Albumin: Day 1 of each cycle (always prior to PM01183 infusion). *
 
Total proteins, total calcium and Mg⁺⁺ will be measured only in those patients with abnormal baseline values.
 
Any patient presenting a grade ≥ 3 treatment-related AE should have all relevant tests re-assessed at least every 48-72 hours until recovery to grade ≤ 2.

3. Pharmacokinetics	
♦ Cycle 1: Eight blood samples (before PM01183 infusion start, 5 min before end of PM01183 infusion and 30 min, 1 hour, 3 hours, 24 hours, 72 hours and 168 hours after the end of PM01183 infusion) will be collected for pharmacokinetic analyses (see details in Section 7.2.1).
 
♦ Cycle 2: Six blood samples (before PM01183 infusion start, 5 min before end of PM01183 infusion and 30 min, 1 hour, 3 hours and 168 hours after the end of PM01183 infusion) will be collected for pharmacokinetic analyses (see details in Section 7.2.1).
	Cycle 1 and Cycle 2.
4. AAGP	One blood sample per cycle.	On Day 1 of Cycle 1 and Cycle 2 (always prior to PM01183 infusion).
5. Pharmacogenetics (only if written informed consent given)	One blood sample.	At any time during the study, but preferably just before treatment start in Cycle 1.
6. Pregnancy test (if women of childbearing potential)	β -hCG (urine or serum). In patients of childbearing potential (except germ cell tumor patients), if β -hCG levels are elevated, pregnancy must be clinically discarded by an additional test (i.e., ultrasound) before any other study procedure. Pregnancy during treatment or within three months from the patient's last PM01183 administration is considered an immediately reportable event.	Day 1 of each cycle (always prior to PM01183 infusion).*
7. ECG	Cardiac rhythm will be identified in ECG intervals of at least 30 seconds of duration, PR interval, QT interval (raw), heart rate and QRS complex.	Repeat if clinically indicated.
8. LVEF	LVEF measured by MUGA or ECHO.	Repeat if clinically indicated.
9. Radiological tumor assessment	Contrast enhanced helical CT-scan or MRI, as clinically indicated.	
Every two cycles from the onset of the study treatment until Cycle 6 and every three cycles thereafter.*
 
Patients showing a response must have a confirmatory assessment at least four weeks later.

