5.8 EVALUATIONS AT END OF TREATMENT

The *end-of-treatment visit* will be scheduled within 30 days (\pm 7 days) after the last PM01183 infusion, unless the patient starts a subsequent antitumor therapy, in which case the end-of-treatment visit should be performed immediately before the start of the new therapy (ideally the day before or the same day).

Patients, regardless of the reason for ending the treatment, will have to undergo at the end of treatment the following assessments:

- Complete physical examination.
- ECOG PS.
- Vital signs.
- Concomitant therapies.
- Laboratory tests (coagulation panel, hematology and biochemistry A and B).
- Pregnancy test, ECG or LVEF assessment (if clinically indicated).
- Radiological tumor assessment (the evaluation should be repeated at EOT visit, if not previously done, and if the reason for treatment discontinuation is other than PD).
- Adverse events.

These evaluations will only have to be repeated for those parameters for which no measurement is available within 10 days before the EOT visit, or for those parameters with values that were out of range in the last assessment (grade \geq 2 according to the NCI-CTCAE v.4).

Adverse events must be reported for 30 days after the last study treatment administration. All serious adverse events (SAEs) occurring within 30 days of the last study treatment administration or until the start of a new antitumor therapy, whichever occurs first, will be reported. Beyond this period of time, only those suspected to be treatment-related SAEs will be reported (Section [7.7.2](#)).

The Sponsor will evaluate all safety information that is spontaneously reported by an Investigator beyond the time frame specified in the protocol.

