4.3 Safety Population

The safety analysis will be based on the “All Treated Patients” analysis set by cohort of tumor types and total population.

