7.2 Clinical Laboratory Evaluation

Laboratory results will be classified according to the NCI-CTCAE v4.

The following hematological values (worst grade per patient and per cycle during treatment) will be displayed: white blood cells count (WBC), neutrophils count, lymphocytes count, platelets count and hemoglobin.

Overall cross tabulation will be presented for the worst grade during treatment *versus* the baseline severity grading of leukopenia, neutropenia, lymphopenia, thrombocytopenia and anemia.

If a grade ≥ 3 neutropenia or thrombocytopenia occurs during a cycle of treatment, the first day it reaches grade 3 or 4 (counting from the start of the cycle) and the duration of the abnormality (i.e., until recovery to grade ≤ 2) will be tabulated.

Similarly, the following biochemical values (worst grade per patient and per cycle during treatment) will be displayed: alanine aminotransferase (ALT), aspartate aminotransferase (AST), total bilirubin, alkaline phosphatase (AP), creatine phosphokinase (CPK), creatinine, gamma-glutamyltransferase (GGT), calcium (corrected by albumin levels), potassium, sodium, magnesium, glucose and albumin.

If a grade ≥ 3 AST or ALT increase occurs during a cycle of treatment, both the day it peaked (counting from the start of the cycle) and the duration of the abnormality (i.e., until recovery to grade ≤ 2) will be tabulated.

Overall cross tabulation will be presented for the worst grade during treatment *versus* the baseline severity grading of biochemical abnormalities.

7.3 Vital Signs, Physical Examination, Left Ventricular Ejection Fraction and Electrocardiogram Findings

Tabulation will be made summarizing the performance status, body weight, left ventricular ejection fraction (LVEF) and electrocardiogram (ECG) abnormalities at baseline and during the treatment, if appropriate, for each cohort and patient.

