8.12 Methods for Handling Missing Data

Missing values will be tabulated with their frequency but they will not be included in the calculation of percentages.

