12.4.4 Laboratory Values over Time

Table 12.4.4.1 Evolution of hematological abnormalities from baseline, worst case per patient.

Table 12.4.4.2 Evolution of hematological abnormalities from baseline, worst case in the first cycle per patient.

Table 12.4.4.3 Evolution of biochemical abnormalities from baseline, worst case per patient.

Table 12.4.4.4 Evolution of biochemical abnormalities from baseline, worst case in the first cycle per patient.

Tables 12.4.4.1 to 12.4.4.4 will have the following pattern:

		Baseline grade*	Worst grade per patient						Total	
			0		1		...		N	%
			N	%	N	%	N	%		
Baseline	Parameter 1	Grade 0								
		Grade 1								
									
	Parameter 2	Grade 0								
		Grade 1								
									
	Grade 0								
		Grade 1								
									

(*) Defined as the last value recorded before or on the date of first infusion.

Table 12.4.4.5 Platelet count time course pattern (summary).

Table 12.4.4.6 Neutrophil count time course pattern (summary).

Tables 12.4.4.5 and 12.4.4.6 will have the following pattern:

	All cycles	First cycle
	N, Mean, Std., Median, Range	N, Mean, Std., Median, Range
Grade $\geq 3^*$ onset day		
Nadir ($\times 10^9/L$)		
Duration of grade ≥ 3 (days)		
Day of recovery to grade 1/2 or baseline values**		

(*) Grade 3 or 4; (**) grade 2 or less.

Table 12.4.4.7 AST time course pattern (summary).

Table 12.4.4.8 ALT time course pattern (summary).

Tables 12.4.4.7 and 12.4.4.8 will have the following pattern:

	All cycles	First cycle
	N, Mean, Std., Median, Range	N, Mean, Std., Median, Range
Grade $\geq 3^*$ onset day		
Peak ($\times ULN$)		
Duration of grade ≥ 3 (days)		
Day of recovery to grade 1/2 or baseline values**		

(*) Grade 3 or 4; (**) grade 2 or less.

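### During treatment cycles, calcium and magnesium are scheduled only in patients abnormal at baseline, so the SAP's per-cycle rates and grade-0 shift rows for them are not incidences in treated patients

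*Protocol*

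**What the plan says.** **Collection.** The Biochemistry B note under the protocol's Schedule of Assessments makes albumin mandatory on Day 1 of every cycle for all patients. Total proteins, total calcium and magnesium, by contrast, "will be measured at baseline and repeated thereafter only in those patients with abnormal baseline values". Protocol 5.7 repeats the restriction for the treatment period: these tests "will be measured only in those patients with abnormal baseline values".

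**End of treatment.** Protocol 5.8 lists, for every patient whatever the reason for stopping, "Laboratory tests (coagulation panel, hematology and biochemistry A and B" among the assessments, without excepting calcium or magnesium. A test is needed when no value exists from the 10 days before the visit. SAP section 7 assigns laboratory results from the EOT visit to the patient's last cycle.

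**Output.** SAP 7.2 displays biochemical results as "worst grade per patient and per cycle during treatment". Its list of analytes ends with "calcium (corrected by albumin levels), potassium, sodium, magnesium, glucose and albumin". It also cross-tabulates worst grade on treatment against baseline grade. The shells are Tables 12.4.2.1 (per patient), 12.4.2.2 (per cycle), 12.4.4.3 (titled "Evolution of biochemical abnormalities from baseline, worst case per patient") and 12.4.4.4 (the same for the first cycle). Safety tables use the All Treated Patients "analysis set by cohort of tumor types and total population".

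**Denominator.** SAP 8.12: "Missing values will be tabulated with their frequency but they will not be included in the calculation of percentages".

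**The concern.** The data collection and the planned tables do not match. AST, ALT, creatinine, sodium, potassium, glucose and albumin are scheduled in every patient, so their worst-grade percentages can be read as rates in treated patients. Calcium and magnesium appear in the same list under the same heading. Yet during the cycles they are scheduled only in patients chosen because the value was already abnormal. Nothing in SAP 7.2 or the table shells gives these two a separate denominator or a caveat.

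Changes in laboratory parameters are a listed safety endpoint, and a reader would take these rows as toxicity rates. They could mislead in either direction. Among patients tested, pre-existing abnormality inflates the figure. If all treated patients form the denominator, new abnormalities that were never looked for deflate it.

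**Working it through.** The plan states no figure for either analyte, so there is nothing to reproduce. The check follows the testing rule through the tables and then illustrates its size.

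**Step 1. What each table contains for a patient normal at baseline**

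- *Table 12.4.2.2 (per cycle).* There is no scheduled value before the last cycle. Under SAP 8.12 those cycles leave the denominator, and the remaining scheduled values come from patients abnormal at baseline.
- *Table 12.4.2.1 (per patient).* The patient contributes at most one scheduled value, from EOT.
- *Table 12.4.4.3 (shift, worst case).* The grade-0 row rests on that same single value.
- *Table 12.4.4.4 (shift, first cycle).* The grade-0 row has no scheduled value unless Cycle 1 was the last cycle.

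If the EOT test is done, the share of such a patient's cycles with a scheduled value is 1/k for k cycles received. For assumed k of 2, 4, 6 and 8 this is 50%, 25%, 17% and 12.5%.

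**Step 2. Size, per 100 treated patients**

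All inputs are assumptions, because the documents give none of them:

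- b = share abnormal at baseline (10% to 30%)
- i = share of baseline-normal patients with a new abnormality on treatment (5% to 20%)
- d = share of those new cases still abnormal at EOT (0 to 100%)

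Baseline abnormalities are taken to persist at re-test.

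The true any-grade rate is b + (1 − b)i. It runs from 0.10 + 0.90 × 0.05 = 14.5% to 0.30 + 0.70 × 0.20 = 44%. The number of new cases is 100(1 − b)i, from 100 × 0.70 × 0.05 = 3.5 to 100 × 0.90 × 0.20 = 18.

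Take b = 20% and i = 10%. New cases are 100 × 0.80 × 0.10 = 8, and the true rate is 20% + 8% = 28%.

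*Schedule note applied literally, with no EOT test in baseline-normal patients.* None of the 8 new cases has a scheduled test. The displayed rate is up to 20/20 = 100% of those tested, or 20/100 = 20% of all treated.

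*EOT test done in everyone, per Protocol 5.8.* The per-patient rate is b + d(1 − b)i:

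| d | New cases seen (of 8) | Displayed rate |
|---|---|---|
| 0 | 0 | 20% |
| 25% | 2 | 22% |
| 50% | 4 | 24% |
| 100% | 8 | 28% |

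The per-patient table is therefore right only if every new abnormality lasts until EOT. Even then, the per-cycle table before the last cycle is unchanged.

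**The case against.** The strongest reply is the EOT visit. A reader might infer from the schedule note that a new calcium or magnesium abnormality in a patient normal at baseline can never reach the on-treatment tables. The documents do not support that. Protocol 5.8 lists Biochemistry B for all patients, SAP section 7 counts the EOT value in the last cycle, and the per-patient denominator may then approach all treated. The value need not be as late as 30 days after the last infusion either, since the visit moves forward if a new antitumor therapy starts. Unscheduled tests can also occur: Protocol 5.7 asks for relevant tests to be repeated after a grade 3 or higher treatment-related event, and clinically significant results are reportable as adverse events.

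There are further safeguards. SAP 8.12 tabulates the frequency of missing values, Listing 12.4.2.5 shows biochemical tests not assessed by patient and cycle, and the shift tables already separate patients by baseline grade. SAP 7.2 never calls the figures incidences.

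All of this stands, and it narrows the point. It does not remove it. One EOT value cannot show an abnormality that has resolved, event-driven tests are not systematic, and a listing of tests not done neither corrects nor labels a percentage. The EOT argument also depends on Protocol 5.8 prevailing over the word *only* in the schedule note, which the documents leave open.

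**Conclusion.** The point holds in a limited form. Per-cycle calcium and magnesium rates before the last cycle describe mainly patients selected for a baseline abnormality. The grade-0 row of Table 12.4.4.3 and the baseline-normal part of Table 12.4.2.1 rest on at most one scheduled value, at EOT. The grade-0 row of Table 12.4.4.4 usually has none. New abnormalities that resolve before EOT have no scheduled test.

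The bias has no single direction. In the illustration, a true 28% could be displayed as up to 100% of those tested during the cycles, or as 20% to 28% of all treated. These figures depend on assumed values of b, i and d, and the protocol does not define an abnormal baseline value by grade or limit. The mismatch itself depends on none of these assumptions.

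It would be wrong to infer a wider effect. These are two descriptive laboratory parameters. Neither is a named re-treatment criterion in Protocol 6.5 or part of a stopping rule in Protocol section 3, and ORR is untouched.

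**What to change.** - **Separate display.** In SAP 7.2 and Tables 12.4.2.1, 12.4.2.2, 12.4.4.3 and 12.4.4.4, take calcium and magnesium out of the pooled percentage display. Report them in two groups: abnormal at baseline and re-tested; and normal at baseline with EOT or unscheduled values only. Give the number tested in each cell and a footnote that the figures are not incidences in treated patients. Keep the second group, because it holds the only scheduled data that can show a new abnormality.
- **Reconcile the protocol.** The schedule note restricts repeat testing to patients abnormal at baseline, while Protocol 5.8 lists Biochemistry B at EOT for all. The answer decides whether the per-patient table is nearly complete or heavily selected.

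The SAP change costs only text, shells and footnotes, with no extra sampling. The reconciliation needs a protocol clarification. Whether to test more patients during treatment is for the sponsor to decide.
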